1. To compare the proportion of study participants who are prescribed appropriate treatment at index visit or within 24 hours of index visit based on the provider assessment conducted at the time of the office/medical visit (Arm 1) to the proportion of study participants who are prescribed appropriate treatment when Xpert® Xpress MVP testing is performed and reported on the day of the office visit (Arm 2).
 - a. Appropriate treatment is defined as CDC recommended or FDA approved treatment based on diagnosis from the self-collected samples. A positive result from both FDA cleared molecular tests (Xpert® Xpress MVP; BD MAX™ Vaginal Panel) will be considered the gold standard for the diagnosis of vaginitis/vaginosis for data analysis.

2.2 Secondary Objectives:

1. To compare the accuracy of provider's diagnosis of vaginitis (usual care) to the diagnosis of vaginitis based on the results of the Xpert® Xpress MVP test at the office/medical visit.
2. To compare the proportion of women who experience resolution of vaginitis symptoms at the two week follow up contact after undergoing evaluation with a novel POC molecular test to the proportion of women with resolution of vaginitis symptoms after evaluation by their provider's usual care.
3. To evaluate participant satisfaction with usual care vs point of care testing for vaginitis. Questionnaires will be administered to all participants at the office visit and approximately two weeks after enrollment.
4. To compare the accuracy of a nonamplified probe-based platform (BD Affirm™ VPIII) that tests for *Candida*, *Trichomonas vaginalis* and *Gardnerella vaginalis* compared to the results of two FDA-cleared molecular tests for diagnosis of vaginitis/vaginosis: two NAAT platforms (Xpert® Xpress MVP; BD MAX™ Vaginal Panel).

2.3 Exploratory Objectives:

1. Assess the impact of vaginitis symptoms on patient quality of life and productivity through use of the Sheehan Disability Scale (SDS), which will be administered at enrollment. Results will be assessed overall and stratified by participant-reported severity based on the Patient Global Impression of Severity (PGIS) instrument.
2. To assess provider satisfaction/treatment confidence with usual care assessment vs Xpert® Xpress MVP testing through the Healthcare Provider Sub Study.

3. Study Population

The inclusion and exclusion criteria in this section will be utilized to ensure the appropriate selection of study participants.

3.1 Recruitment:

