7.3 Secondary and Exploratory Endpoint Analyses

Patient and Provider satisfaction with usual care versus point of care testing will be evaluated on a 5-point Likert scale with 1 being very satisfied to 5 being very dissatisfied. Responses will be dichotomized for analyses (very satisfied and satisfied versus all others). Differences in patient and provider satisfaction with and the proportion of women who experience resolution of vaginitis symptoms after treatment based on usual care and point of care testing will be evaluated using Fisher's exact test.

A positive result from both of the two FDA cleared molecular tests (Xpert® Xpress MVP; BD MAX™ Vaginal Panel) will be considered the gold standard for the diagnosis of vaginitis/vaginosis for analysis. Samples yielding discordant results will be retested using the reserve sample. Samples which are discordant after retesting will be evaluated separately.

Fisher's exact test will be used to compare the provider's diagnosis of vaginitis based on usual care to the diagnosis based on the results of point of care testing. The sensitivity, specificity, negative and positive predictive values of the BD Affirm™ VPIII test for *Candida*, *Trichomonas vaginalis* and *Gardnerella vaginalis* will be calculated and compared to those of the two FDA-cleared tests using the test for equality of proportions.

Patient quality of life and productivity will be assessed using the Sheehan Disability Scale (SDS) where 0 indicates no functional impairment and 30 high functional impairment. Descriptive statistics will be used to assess overall SDS scores. Differences in SDS scores by participant-reported severity will be evaluated using Kruskal-Wallis (continuous SDS score) and Fisher's exact (categorized SDS score) tests.

[figure not shown]
8. Costs and Payments:

The cost for the testing for vaginitis using the self-collected molecular methods will be covered by the study in both arms of the study. The cost of routine clinical care visits, which may include other diagnostic testing will not be covered by the study. Treatment may be prescribed by the healthcare provider according to usual care; the cost of this treatment will not be covered by the study.

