8.1 FUNDING

Funding for this investigator-initiated study is being provided by Cepheid.

Schedule of Participant Study Visits and Evaluations:

Study Procedures	Visit 1	Visit 2
Visit type	Enrollment	Follow-Up Telephone Contact
Time	0	2 weeks
Length of Visit	20 min	10 min
Informed consent	x	
Eligibility	x	
PGIS (Symptom severity)	x	
PGIC (Symptom severity – change)		x
Sheehan-disability-scale (Productivity; daily activity)	x	
Self-collect three vaginal swabs	x	
Randomization	x	
Provide Xpert® Xpress MVP results to provider – Arm 1		x
Provide Xpert® Xpress MVP results to provider – Arm 2	x	
Diagnosis based on usual care at time of visit – Arm 1	x	
Diagnosis based on Xpert® Xpress MVP result at time/day of visit – Arm 2	x	
Participant Compensation		x
Collect/update/review contact/locator information	x	
Chart review to extract visit details, diagnosis, tx and results*	x	x

*May occur up to 4 weeks following office (enrollment/index) visit

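### Secondary objective 1 asks which diagnosis is more accurate, but the planned Fisher's exact test names no accuracy measure and the only stated gold standard includes MVP

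*Combined protocol and SAP*

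**What the plan says.** Section 2.2, item 1, sets the aim: "To compare the accuracy of provider's diagnosis of vaginitis (usual care) to the diagnosis of vaginitis based on the results of the Xpert® Xpress MVP". The word that matters is accuracy.

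Section 7.3 gives the whole analysis in one sentence: "Fisher's exact test will be used to compare the provider's diagnosis of vaginitis based on usual care to the diagnosis based on the results", where the results meant are those from the point-of-care test. It does not state the analysis set (within Arm 1, or Arm 1 against Arm 2), the unit (per infection or per woman), an accuracy measure or an interval. The sentence that follows it does name sensitivity, specificity and predictive values, but for BD Affirm.

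The paragraph just before defines the reference: "A positive result from both of the two FDA cleared molecular tests (Xpert® Xpress MVP; BD MAX™ Vaginal Panel) will be considered the gold standard". On disagreement between the two tests it adds "Samples yielding discordant results will be retested using the reserve sample" and then "Samples which are discordant after retesting will be evaluated separately".

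The schedule of visits lists "Diagnosis based on usual care at time of visit – Arm 1" and places the MVP-based diagnosis in Arm 2. Sections 4.1 and 5 have MVP run on every Arm 1 sample as well, with the result withheld until after the two-week call. Section 4.2 has BD MAX run in both arms, and it leaves Arm 2 providers free not to follow MVP.

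**The concern.** There are two separate problems.

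First, the named test does not by itself compare accuracy. Arm 1 yields two diagnoses per woman. Fisher's test on their cross-table asks whether they are associated, so a very small p-value means that they go together. A reader expecting a test of difference would take the opposite message. Between arms the test suits independent groups, but the plan does not say which proportion is compared. The proportion diagnosed and the proportion correctly diagnosed are different questions.

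Second, the only stated reference requires a positive MVP result. A test judged against a standard that it helps to define has an advantage unrelated to its real performance. The manufacturer of MVP funds the study (section 8.1), so this would be an obvious criticism of any published accuracy comparison.

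At stake is whether secondary objective 1 has an interpretable answer, and whether the form of the analysis is fixed before the data are seen.

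**Working it through.** **The plan's own figure.** The only design figure is in section 7.1: 91% power for the primary endpoint with 150 per arm, 75% against 90%, Fisher's test, two-sided 0.05. Full enumeration of two Binomial(150) arms gives 91.6%, so it reproduces. It has no bearing on secondary objective 1, for which no figure is stated.

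**Inputs.** 150 women in Arm 1 (7.1). Expected prevalence: BV 30%, VVC 34%, TV 7% (3.1). MVP agreement with laboratory molecular tests: positive 93.6–99.0%, negative 92.1–99.8% (section 1). Assumptions: these ranges apply to agreement with BD MAX, and the cell counts below are illustrative.

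**Step 1: Fisher within Arm 1.** Provider-by-MVP tables, n = 150. McNemar here uses the same table, with no external reference.

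| Both + | MVP + only | Provider + only | Both − | Agreement | Fisher p | Exact McNemar p |
|---|---|---|---|---|---|---|
| 45 | 0 | 0 | 105 | 150/150 = 100% | 2 × 10⁻³⁹ | 1.0 |
| 35 | 10 | 10 | 95 | 130/150 = 86.7% | 2 × 10⁻¹⁶ | 1.0 |
| 31 | 14 | 16 | 89 | 120/150 = 80.0% | 2.5 × 10⁻¹⁰ | 0.86 |
| 14 | 31 | 31 | 74 | 88/150 = 58.7% | 0.85 | 1.0 |

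The last row is a provider who diagnoses at random in about 30% of women. Fisher is most significant when the two diagnoses are identical and non-significant when the provider is guessing. McNemar on this table is no remedy: it compares positivity rates (47/150 against 45/150 in the third row) and gives 1.0 for both perfect and random providers. It addresses accuracy only when applied among reference-positives or among reference-negatives.

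**Step 2: Fisher between arms.** On the proportion diagnosed, 45/150 against 45/150 gives p = 1.0 however many of those diagnoses are wrong. On the proportion correct, the groups are independent and the test is valid.

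**Step 3: the reference.** Let π be prevalence by BD MAX, a the positive agreement and s the negative agreement. The cells are: both positive πa; MVP only (1−π)(1−s); BD MAX only π(1−a); both negative (1−π)s.

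- Discordants excluded: MVP sensitivity = πa/πa = 100%; specificity = (1−π)s/[(1−π)s] = 100%, for any a and s.
- Discordants counted as reference-negative: sensitivity is still 100%; specificity = 1 − (1−π)(1−s)/(1−πa). At π = 0.07, a = 0.936, s = 0.921 this is 1 − 0.07347/0.93448 = 92.1%. At a = 0.990, s = 0.998 it is 99.8%.
- BD MAX alone: sensitivity = a (93.6–99.0%) and specificity = s (92.1–99.8%). The composite with discordants excluded therefore raises MVP's sensitivity by 1.0 to 6.4 points and its specificity by 0.2 to 7.9 points.
- Discordance before retest = (1−π)(1−s) + π(1−a). At π = 0.07 the extremes are 0.07347 + 0.00448 = 7.8% (about 23 of 300) and 0.00186 + 0.00070 = 0.3% (about 1 of 300). The other two prevalences fall between these.

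**Step 4: what a fixed 100% does.** If one side were 150/150 by construction, a provider figure of 145/150 gives Fisher p = 0.060 and 144/150 (96%) gives p = 0.030. The test would only ask whether providers fall short of 100%.

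**Step 5: precision by target in Arm 1.** Expected positives: BV 0.30 × 150 = 45; Candida 0.34 × 150 = 51; TV 0.07 × 150 = 10.5. With k discordant pairs all in one direction, exact McNemar p = 2 × 0.5^k: 0.0625 at k = 5 and 0.031 at k = 6. A TV sensitivity difference therefore needs at least 6 one-directional pairs out of about 10 positives.

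**The case against.** The strongest reply is that the between-arm reading is the natural one. Section 7.3 labels the arms as usual care and point of care testing, and the schedule splits the two diagnoses between arms in the same way. On that reading the groups are randomized and independent, and Fisher's test on the proportion correct is sound. This stands. A reader might infer that no reading of the plan can answer the objective, but the documents do not support that. What remains is that the plan never names the proportion correct. That comparison would also measure MVP-informed provider diagnosis, not MVP itself, because Arm 2 providers may depart from the result.

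A reader might also infer that MVP is certain to score perfectly. That goes too far as well. The Fisher sentence names no reference, so applying the composite is an inference from the preceding paragraph. The literal definition fixes sensitivity only; specificity is fixed only when discordants are excluded, and the plan says that they are evaluated, though separately. A retest could change the MVP call, leaving the original point-of-care result wrong. A provider-recorded Arm 2 diagnosis is not fixed at all. The direction of the bias survives these points. No MVP-free reference is given for this objective, and using MVP itself as the comparator would be equally circular.

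BD MAX alone is not a clean truth either. Section 1 gives it 90.5% sensitivity and 85.8% specificity for BV, and its BV targets overlap with those of MVP. That limits the fix but does not restore the composite.

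**Conclusion.** The concern holds in this form: the stated analysis of secondary objective 1 does not specify a comparison of accuracy, and the only stated gold standard favours MVP.

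Within Arm 1, Fisher's test answers a question about association. Between arms, it is valid only for an outcome that the plan does not name. With the composite reference, MVP's final-result sensitivity is 100% by construction, and its specificity is too when discordants are excluded. The inflation of MVP's own figures is as calculated in Step 3, if the Background agreement ranges carry over to BD MAX and before any discordance is resolved by retest. Its effect on the provider-minus-MVP difference cannot be derived from the documents, because dropping discordant samples may change the provider's figure too.

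A reader might infer that the primary result is compromised. The Fisher point does not support this: section 7.2 compares independent arms on a stated proportion, and the power reproduces.

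**What to change.** In section 7.3, replace the Fisher sentence for secondary objective 1 with the following.

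- **Main analysis, Arm 1.** For each target (BV, Candida, TV), report sensitivity and specificity of the provider diagnosis and of the original MVP result against BD MAX alone, keeping samples on which MVP and BD MAX disagree. Compare provider and MVP within woman by McNemar's test, separately among BD MAX positives (sensitivity) and BD MAX negatives (specificity), with 95% CIs for the paired differences.
- **Between arms, if wanted.** Use Fisher's exact test on the proportion correctly diagnosed against BD MAX, described as usual-care against MVP-informed provider diagnosis.
- **Sensitivity analysis.** Report the result against the composite reference, labelled as including MVP.

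The cost is wording only; every result needed is already planned. The downsides should be stated. MVP accuracy will fall below 100% and carry an interval. BD MAX is imperfect for BV and shares BV targets with MVP, so some bias toward MVP may remain. The TV sensitivity comparison, on about 10 positives, will be imprecise and is better reported as an estimate with its interval than relied on as a test.

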Study Population:	Individuals 14 years and older, assigned female sex at birth, who are seeking care at a UPMC Magee-Womens Hospital (MWH) participating PAT study office complaining of symptoms of vaginitis
Study Duration:	Approximately two weeks of follow-up per participant with a projected accrual period of approximately 12 months
Study Sites:	Obstetric/gynecologic (OB/GYN) practices/offices located within UPMC Magee-Womens Hospital (MWH) and outpatient centers affiliated with the Department of OB/GYN or MWH
Study Design:	Two arm, randomized, single center trial of usual care vs. Xpert® Xpress MVP (multiplex vaginal panel; Cepheid, Sunnyvale, CA) directed care for vaginitis diagnosis and treatment

Individuals who are complaining of vaginitis symptoms and are seeking care at one of the PAT study participating offices/departments within or affiliated with MWH will be invited to participate. In this study, the office visit will serve as the enrollment (index) visit. Following informed consent, participants will complete a brief questionnaire and self-collect three vaginal swabs for three tests that are FDA-cleared for vaginitis diagnosis: Xpert® Xpress MVP, BD MAX™ Vaginal Panel (Becton-Dickinson, Franklin Lakes, NJ), and BD Affirm™ VPIII Microbial Identification Test (Affirm™ VPIII; Becton-Dickinson). Participants will be randomized (1:1) into one of two arms after collecting swabs.

In Arm 1, vaginitis diagnosis and treatment will be based on usual provider evaluation and treatment during the office visit. The Xpert® Xpress MVP test will be batched with delayed results made available to the provider following the participant's 2-week study follow-up telephone contact.

In Arm 2, the Xpert® Xpress MVP test will be run in real time as a point of care (POC) test at the time of the office visit and the results will be made available to the provider in approximately one hour. Providers will be asked to use the MVP test result for diagnosis and treatment of the participant.

All participants, regardless of arm, will complete a follow-up telephone contact approximately two weeks after their office/medical visit to assess symptom resolution and satisfaction.

The study will include review and collection of electronic medical record information related to the office/medical visit (i.e., evaluation, testing, diagnosis and treatment).

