Advances in highly sensitive nucleic acid amplification testing (NAAT) for the microorganisms associated with vaginal infections have provided an opportunity to employ more sensitive and specific methods for diagnosis of these infections. The BD MAX™ Vaginal Panel provides results by an algorithmic analysis of molecular DNA detection of *Lactobacillus* species (*L. crispatus* and *L. jensenii*) in addition to *Gardnerella vaginalis*, *Fannyhessea vaginae* (formerly *Atopobium vaginae*), *Amygdalobacter indicum* (formerly BVAB2), and *Megasphaera lornae* (formerly *Megasphaera* type 1). This test has 90.5% sensitivity and 85.8% specificity for BV diagnosis, compared with Amsel criteria and Nugent score²⁰. It also provides results for *Candida* species and *T. vaginalis*. The Aptima® BV (Hologic, Inc., San Diego, CA) detects *G. vaginalis*, *Fannyhessea vaginae* (*A. vaginae*), and certain *Lactobacillus* species including *L. crispatus*, *L. jensenii*, and *L. gasseri*, with sensitivity and specificity ranging from 95.0% to 97.3% and 85.8% to 89.6%, respectively (using either clinician- or patient-collected vaginal swabs)¹².

The Xpert® Xpress MVP is a new on-demand NAAT developed by Cepheid, to aid in the diagnosis of vaginal infections in women with a clinical presentation of vaginitis/vaginosis. The test is simple to use and detects DNA targets from anaerobic bacteria associated with BV (*A. vaginae*, *A. indicum*, and *M. lornae*), *Candida* species and *T. vaginalis*. Cepheid has recently received 510(k) clearance and CLIA Waiver for Xpert® Xpress MVP. When compared to moderately complex nucleic acid amplification tests performed in a laboratory by trained technologists, the Xpert® Xpress MVP demonstrated high positive percent agreement ranging from 93.6 to 99.0%, and negative percent agreement ranging from 92.1% to 99.8% for both clinician-collected samples and patient-collected samples²¹.

The overarching objective of the proposed study is to evaluate whether same day testing using the Xpert® Xpress MVP test in a patient care setting results in a higher degree of appropriate treatment of vaginitis compared to standard of care for women having vaginitis symptoms.

2. Study Objectives

2.1 Primary Objective:

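### Secondary objective 4 tests BD Affirm against the two assays that make up its own reference standard, so the planned p-values do not compare the accuracy of the tests

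*Combined protocol and SAP*

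**What the plan says.** Secondary objective 4 (Section 2.2) sets the accuracy of BD Affirm VPIII "compared to the results of two FDA-cleared molecular tests for diagnosis of vaginitis/vaginosis: two NAAT platforms", namely Xpert MVP and BD MAX. Section 7.3 gives the analysis: Affirm's sensitivity, specificity, NPV and PPV "will be calculated and compared to those of the two FDA-cleared tests using the test for equality of proportions".

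Section 7.3 also fixes the reference: "A positive result from both of the two FDA cleared molecular tests (Xpert® Xpress MVP; BD MAX™ Vaginal Panel) will be considered the gold standard". Discordant samples are retested from the reserve sample, and then: "Samples which are discordant after retesting will be evaluated separately". No other reference standard is given for this objective.

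The study design summary has participants "self-collect three vaginal swabs for three tests that are FDA-cleared for vaginitis diagnosis", so every woman contributes a result on each assay. No paired method is named anywhere in the plan.

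On targets, Section 7.3 says that the measures for the Affirm "test for *Candida*, *Trichomonas vaginalis* and *Gardnerella vaginalis* will be calculated". Section 1 lists MVP's BV targets as *A. vaginae*, *A. indicum* and *M. lornae*. BD MAX uses *G. vaginalis* as one input to an algorithm and, by Section 4.2, reports bacterial vaginosis.

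**The concern.** A test cannot be judged against a standard of which it is a part. Any sample positive on the reference is positive on MVP and on BD MAX by definition, so neither can miss a case. Comparing Affirm's sensitivity with theirs asks only whether Affirm falls short of a fixed 100%. A reader of the results would take the p-value as evidence that the amplified tests are more accurate, when the design could not have shown otherwise.

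Two smaller matters go with this. The three results on each woman are correlated, and the named test usually assumes independent samples. Also, the plan does not say how an Affirm *G. vaginalis* result is scored against a reference that is a BV result.

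At stake is the interpretation of one secondary objective.

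**Working it through.** **Plan's own figures.** The documents give no calculated figure for the Affirm comparison. The only calculated design figure is the 91% power for the primary endpoint (Section 7.1: 75% v 90%, 150 per arm, Fisher's exact, two-sided 0.05). Full enumeration gives 91.6%, so it reproduces. It does not bear on this point.

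**Step 1: what the reference fixes.** Cross-classify samples by the two NAATs: *a* = both positive, *b* = MVP only, *c* = BD MAX only, *d* = both negative. The reference is positive in *a* alone.

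| Measure | MVP, discordants kept as negative | BD MAX, discordants kept as negative | Either, discordants set aside |
|---|---|---|---|
| Sensitivity | a/a = 100% | a/a = 100% | 100% |
| NPV | (c+d)/(c+d) = 100% | (b+d)/(b+d) = 100% | 100% |
| Specificity | (c+d)/(b+c+d) | (b+d)/(b+c+d) | d/d = 100% |
| PPV | a/(a+b) | a/(a+c) | a/a = 100% |

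Sensitivity and NPV are fixed under both readings. Specificity and PPV fall below 100% only through *b* and *c*, that is, through disagreement between the two NAATs.

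**Step 2: illustration for BV.** Inputs: prevalence 30% (Section 3.1); BD MAX 90.5% sensitivity and 85.8% specificity (Section 1); MVP 93.6% and 92.1%, the lower ends of the agreement ranges in Section 1, used here as if they were accuracies. Conditional independence is assumed, and retesting is ignored.

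- a = 0.3×0.936×0.905 + 0.7×0.079×0.142 = 0.262
- b = 0.3×0.936×0.095 + 0.7×0.079×0.858 = 0.074
- c = 0.3×0.064×0.905 + 0.7×0.921×0.142 = 0.109
- d = 1 − a − b − c = 0.555

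MVP's assumed 93.6% sensitivity and BD MAX's 90.5% both appear as 100%. With discordants kept as negative, specificity is 0.664/0.738 = 90% (MVP) and 0.629/0.738 = 85% (BD MAX). With discordants set aside, both are 100%. Discordant samples are b + c = 18%, about 55 of 300, before retesting. With more favourable assumed accuracies (MVP 99.0%/99.8%, BD MAX 95%/95%) the share is about 5%, or 16 of 300. The unstated rule for discordants could therefore matter.

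**Step 3: the named test.** Expected positives among 300, from the Section 3.1 prevalences: BV 90, VVC 102, TV 21. Treat these as the reference positives. The comparator is then 90/90 for BV. With 5 Affirm misses (85/90):

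- Pooled z: p̄ = 175/180; SE = √[(175/180)(5/180)(2/90)] = 0.0245; z = 0.0556/0.0245 = 2.27; p = 0.023.
- Exact McNemar, 5 v 0 discordant pairs: 2 × 0.5⁵ = 0.0625.
- Asymptotic McNemar: z = √5 = 2.24; p = 0.025.

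The fewest misses giving p < 0.05 are 4 (pooled z), 4 (asymptotic McNemar), 6 (exact McNemar), and for unpaired Fisher 6 for BV and VVC or 5 for TV. For sensitivity, much of the gap is thus asymptotic versus exact rather than pairing as such. The choice matters most for TV: with 21 positives and an assumed Affirm sensitivity of 80%, the chance of rejecting is 63% (pooled z), 41% (Fisher) and 23% (exact McNemar). For BV and VVC at 80% or below, all of these tests reject almost surely.

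**Step 4: targets.** MVP does not list *G. vaginalis* as a target, and BD MAX reports BV. Neither gives a *G. vaginalis* call against which Affirm's could be scored directly.

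**The case against.** The useful part of the analysis survives. Affirm's sensitivity, specificity, PPV and NPV against concordant NAAT results are sensible estimates and the plan already calculates them; only the added test is defective. This stands, and it limits the weight of the point.

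Four stronger readings are tempting, and the documents do not support them.

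- *All four NAAT measures are fixed at 100%.* Section 7.3 says only that persistent discordants are looked at separately, not that they leave the denominators. This is certain for sensitivity and NPV only.
- *The plan specifies an unpaired test.* It does not use that word, and McNemar's test is itself a test of equality of correlated proportions. Independence is inferred from the usual meaning of the named test; the fair statement is that pairing is not addressed.
- *Ignoring pairing would hide a real difference.* Examples that show this need a comparator sensitivity below 100%, which cannot occur under this reference. With the comparator at 90/90, the pooled z-test rejects sooner than exact McNemar, not later.
- *The* Gardnerella *comparison does not exist, because MVP does not detect the organism.* Section 7.3 names the three organisms as Affirm's targets, and Section 4.2 sets them beside BD MAX's *Candida*, *T. vaginalis* and bacterial vaginosis. Scoring *G. vaginalis* as BV is very probably intended; what is missing is the sentence that says so.

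**Conclusion.** The comparison is wrong as written, for secondary objective 4 only. MVP and BD MAX have 100% sensitivity and NPV by construction, and 100% specificity and PPV as well if persistent discordants are set aside. The null hypothesis for sensitivity is then that Affirm never misses a reference-positive sample, which a single miss contradicts, so the p-value carries no information on relative accuracy. This follows from the definitions and needs no numerical assumption.

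The pairing point is secondary and its effect on sensitivity is modest: p = 0.023 against 0.0625 in the example, which assumes 90 BV positives and 5 misses. The illustrative specificities and discordance rates rest on the accuracies and conditional independence assumed above.

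A reader might infer that the trial's main result is compromised. It is not: the primary comparison and its power do not use this test. The point deserves correction before analysis, but it is not a condition for the trial to go ahead.

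**What to change.** In Section 7.3:

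1. Report Affirm's sensitivity, specificity, PPV and NPV against the concordant-NAAT reference with exact 95% confidence intervals, and delete the test against MVP and BD MAX.
2. State whether samples still discordant after retesting enter the denominators, and show the results both ways.
3. State that Affirm's *G. vaginalis* result is scored as its call for BV, because neither NAAT reports *G. vaginalis*.
4. If a head-to-head is still wanted, label it secondary and compare Affirm with MVP against BD MAX alone by paired methods: McNemar's test for sensitivity and specificity, and a paired generalised score test for PPV and NPV, whose denominators differ between tests. State the limitation: BD MAX is an imperfect BV reference (90.5% sensitivity, 85.8% specificity in Section 1), and all three MVP BV targets are also among its inputs, so shared errors may favour MVP, the funder's assay.

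The cost is some plan wording and a few lines of code; no new data are needed. The downside is that the NAATs no longer carry a comparative p-value or a 100% figure.
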